Hypothesis: We hypothesize that large-scale metabolomics profiling on dried blood spots (DBS), in fibroblasts, urine, stool, and serum will allow more discriminate screening and diagnosis of inborn errors of metabolism and lead us to better understanding the pathophysiology in metabolomic abnormalities). We will also utilize different culturing and measuring conditions to help us to develop new therapies. The overall goal of this study is to develop a novel high-throughput screening and diagnostic platform for understanding the pathology of inborn errors of metabolism and assessing different conditions through spiking samples with sugars or mimicking changes in diet during measurement by using global metabolomic profiling. Metabolomic profiling is a technique that provides a comprehensive view of metabolic pathways and therefore allows for more discriminate evaluation of analyte abnormalities. To perfect this platform, different human samples including fibroblasts, serum, urine and DBS are required. In particular, samples with known disease states have significant utility as they will aid in the mapping of metabolic pathway perturbations in their respective diseases.

Aims, purpose, or objectives:

Aim 1: To evaluate the metabolic background of disorders by using dried blood spots, fibroblasts, serum and urine from clinical residual samples stored in BGL and from patients collected under IRB 19-005187.

- a. Current disorders using stored blood spots, fibroblasts, serum and urine that need improvement in diagnostics

Aim 2: Improve follow-up and accurate diagnosis of inborn errors of metabolism.

- a. Better understanding of biomarkers
- b. Better understanding culturing and measuring conditions

Aim 3: Measurement of samples under different conditions (mimicking dietary intake and changes or adding sugars to the samples prior measurement)

- a. Standardize measurements
- b. Asses the effect of dietary conditions on measurements to evaluate dietary therapy

Background (*Include relevant experience, gaps in current knowledge, preliminary data, etc.*):

Current metabolic disagnostics employs procedures such as tandem mass spectrometry (MS/MS), fluorometric assays and enzymology testing to test for inborn errors of metabolism. These tests may produce false positives and require further testing before a diagnosis can be made, costing families additional time and money before being provided answers about the health of their child. Using global metabolomic profiling, metabolic pathways can be examined more comprehensively to evaluate any irregularities in analyte levels. We hypothesize that global metabolomics profiling can provide improvements to the process of finding and diagnosing inborn errors of metabolism.

Data in this study will be taken from anonime residual samples from Mayo Clinic patients with known diseases, available through BGL, and from patients consented under IRB 19-005187. The DBS will be the primary identifier, Based on the prior diagnosis of the samples, metabolomics data will be collected and will be analyzed to see if the metabolomics profile can pick up the abnormality using the DBS, serum, urine or fibroblast samples. It has already been shown that metabolomics profiling can detect an array of inborn errors of metabolism with more details on pathophysiology under different conditions.

Subject Information – charts, records, images, or specimens are considered ‘subjects’

Target accrual: *Proposed number of subjects to be included in your study at your site. “Subjects” may include Mayo Clinic charts, records, or specimens, and/or charts, records, or specimens received at Mayo Clinic from external sources for collaborating analysis by the investigator under this IRB application: 160*

Subject population: The target population for this study includes anonime residual samples of individuals affected by inborn errors of metabolism.

Inclusion Criteria: All individuals with specimens in BGL or consented to future research under IRB 19-005187..

Exclusion Criteria: None..

Study Design

Methods: *Describe, in detail, the research activities that will be conducted under this protocol:* The work we propose involves the analysis of existing DBS, fibroblast, serum, stool, and urine samples of Mayo Clinic patients provided by the BGL lab or by the IRB 19-005187. Mayo Clinic will perform untargeted global analysis of metabolites present in the samples. We will then use the analysis to diagnose the inborn errors of metabolism in these individuals as well as identify biomarkers for these disorders.

Resources: *Describe the available resources to conduct the research (personnel, time, facilities, mentor commitment, etc.):* We will utilize DBS, fibroblasts, serum, stool, and urine provided by the BGL clinical laboratory. Specimens will also come from IRB 19-005187. Metabolomic analysis will be performed by staff members at Mayo Clinic.

Check all that apply. If none apply, leave blank:

- This is a multisite study involving Mayo Clinic and non-Mayo Clinic sites.
When checked, describe the research procedures/activities being conducted **only** at Mayo Clinic:
- Mayo Clinic staff will be engaged in research activity at a non-Mayo Clinic site. *When checked, provide the location and a detailed description of the Mayo Clinic research staff involvement.*
- This study is to establish and/or maintain an ongoing database or registry for research purposes only.
- The research involves contact or interaction with subjects, for example, surveys, questionnaires, observation, blood draw.
- The study involves audiotaping or videotaping

Blood Collection

If this study involves prospective blood collection by finger, heel, ear stick or venipuncture, complete the following:

From healthy, non pregnant, adult subjects who weigh at least 110 pounds. For a minimal risk application, the amount of blood drawn from these subjects may not exceed 550ml in an 8 week period and collection may not occur more frequently than 2 times per week.

Volume per blood draw: _____ ml

Frequency of blood draw (e.g. single draw, time(s) per week, per year, etc.) _____

From other adults and children considering age, weight, and health of subject. For a minimal risk application, the amount of blood drawn from these subjects may not exceed the lesser of 50 ml or 3 ml per kg in an 8 week period, and collection may not occur more frequently than 2 times per week.

Volume per blood draw: _____ ml

Frequency of blood draw (e.g. single draw, time(s) per week, per year, etc.) _____

Review of Chart, Images, Specimens

Provide the date range for collection of data and/or specimens that will be included in your research dataset. (Example: 01/01/2000 to 12/31/2012)

Date range: 01/01/1980 to present

Check all that apply:

This study involves only data and/or specimens that exist at the time this application is submitted to the IRB (IRB submission date). No data or specimens will be collected beyond this date.

This study involves only data and/or specimens that will be collected after submission to the IRB.

The study involves data and/or specimens that exist at the time of submission to the IRB **and** data and/or specimens that will be collected after submission to the IRB, for example a study that includes collection of existing data and prospective collection of specimens.

Data and/or specimens used in this study are collected under another IRB protocol. *When checked, provide the IRB number(s) from which the research material will be obtained and check the box below to attest that subjects have provided consent for future use of their data and/or specimens, as described in this protocol.*

19-005187

Subjects have provided consent for use of their data and/or specimens, as described in this protocol.

Other data sources will be utilized in this study. When checked, provide all data sources:

Data Confidentiality, HIPAA Subject Identifiers

Review the list of subject identifiers below and, if applicable, check the box next to each subject identifier being recorded at the time you are collecting/abstracting data/specimens for use in this study.

Subject Identifiers: Individually identifiable information, including demographic data, that identifies the individual or for which there is reasonable basis to believe it can be used to identify the individual. NOTE: Identifiers apply to subjects enrolled in your study and to the subject’s relatives, household members, employers, etc.

Internal refers to subject identifiers that will be included in the dataset maintained by the study team.

External refers to subject identifiers that will be shared with persons outside of the immediate study team, for example, sent to an external collaborator or shared with a national registry.

SUBJECT IDENTIFIERS Check all that apply	INTERNAL IDENTIFIER	EXTERNAL IDENTIFIER
Name		
Social Security number		
Medical record/patient registration number, lab accession, specimen or radiologic image number		
Study number, subject ID, or any other unique identifying number, characteristic or code that can be used to link the identity of the subject to the data	X	
Dates: All elements of dates [month, day, and year] directly related to an individual. Their birth date, date of death, date of diagnosis, etc. Note: Recording a year only is not a unique identifier.		
Medical device identifiers and serial numbers		
Biometric identifiers, including finger and voice prints, full face photographic images and any comparable images		
Web Universal Resource Locators (URLs), Internet Protocol (IP) address numbers, email address		
Street address, city, county, precinct, zip code, and their equivalent geocodes		
Phone or fax numbers		
Account, member, certificate or professional license numbers, health beneficiary numbers		
Vehicle identifiers and serial numbers, including license plate numbers		
If None of the above identifiers will be recorded or maintained in the	 None	 None

dataset and/or sent outside of the study team, please check “None”.

Statistical Information

Note: Power analyses and study endpoints are not needed for a pilot or feasibility studies.

No statistical information. *If checked, please explain:* Due to this study being a chart review study, no statistical analysis will be performed.

Statistical Considerations

Power Statement: The results will be compared directly with the known results of the DBS (negative or positive for an inborn error of metabolism) therefore it will be clear for each sample whether the analysis showed the correct result.

Data Analysis Plan: As above.

Endpoints

Primary: To evaluate whether untargeted metabolomics profiling on dried blood spots can detect inborn errors of metabolism

Secondary: Can untargeted metabolic profiling give a comprehensive and discerning view of the patient’s metabolism to aid interpretation of equivocal results.

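### The protocol rules out any statistical analysis because it is a chart review, yet it runs new diagnostic assays and sets a detection endpoint that is left without an estimate or interval

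*Protocol*

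**What the plan says.** Under Statistical Information, as the explanation attached to the form item for having no statistical information, the protocol writes: "Due to this study being a chart review study, no statistical analysis will be performed". The extracted text does not show whether the box itself was ticked.

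The fields that follow are nevertheless filled in:

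- **Power Statement:** "The results will be compared directly with the known results of the DBS (negative or positive for an inborn error of metabolism"), so that each sample can be seen to be correctly or incorrectly called.
- **Data Analysis Plan:** only a reference back to the Power Statement.
- **Primary endpoint:** "To evaluate whether untargeted metabolomics profiling on dried blood spots can detect inborn errors of metabolism".

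Elsewhere the study is described as laboratory work with a diagnostic purpose. Hypothesis section: "The overall goal of this study is to develop a novel high-throughput screening and diagnostic platform". Methods: "Mayo Clinic will perform untargeted global analysis of metabolites present in the samples", and then "We will then use the analysis to diagnose the inborn errors of metabolism in these individuals".

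Subject Information gives a target accrual of 160, without a split by known status, disorder or specimen type. A note printed on the form says: "Power analyses and study endpoints are not needed for a pilot or feasibility studies".

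**The concern.** The reason given for having no analysis is that this is a chart review. Running a new assay on stored specimens and comparing its calls with a reference diagnosis is an evaluation of a diagnostic test, so the reason does not fit the study. The rule drawn from it also conflicts with the endpoint stated in the same part of the protocol: whether a test can detect disease is answered by a proportion, and a proportion from a finite sample carries uncertainty.

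At stake is the primary endpoint itself. With no summary measure named and analysis expressly excluded, a reader would receive individual calls but no detection rate and no indication of how far that rate might differ in future samples, which is what a screening platform has to show.

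The Background motivates the work by the false positives of current tests, so errors among unaffected samples matter as much as missed cases, and sensitivity and specificity need separate reporting. Whether specificity can be estimated at all is unclear. The target population is described as "anonime residual samples of individuals affected by inborn errors of metabolism", while the inclusion criteria admit everyone with specimens from the two sources and the Power Statement expects known negatives as well as positives.

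**Working it through.** **1. The statements side by side**

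| Place in the protocol | What it implies |
|---|---|
| Statistical Information, explanation | Chart review; no analysis |
| Hypothesis; Study Design, Methods | New assays, used to diagnose, for a screening and diagnostic platform |
| Power Statement | Each call compared with known positive or negative status |
| Data Analysis Plan | Nothing beyond the Power Statement |
| Endpoints, Primary | Can DBS profiling detect inborn errors of metabolism |

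The first row conflicts with the second on what kind of study this is, and with the last three on whether anything is to be analysed. The comparison would let positives and negatives be tabulated separately, but no rate or interval is named.

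**2. Is there a stated figure to reproduce?**

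No. The only size given is 160 subjects. It comes with no error rate, power, expected detection rate or precision target, so it can be neither confirmed nor refuted.

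**3. How much uncertainty goes unreported?**

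Stated input: 160 subjects (Subject Information). Assumed inputs: the number *n* of known-positive DBS, one per subject, and the observed detection rate. Neither is in the protocol.

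Exact (Clopper-Pearson) 95% interval for *x* correct calls out of *n*:

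- lower limit = 0.025 quantile of Beta(*x*, *n* − *x* + 1)
- upper limit = 0.975 quantile of Beta(*x* + 1, *n* − *x*)

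For example, with 144 of 160, Beta(144, 17) gives 84.3% and Beta(145, 16) gives 94.2%.

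| Assumed rate | Correct / n | Exact 95% interval | Width (points) |
|---|---|---|---|
| 90% | 144/160 | 84.3% to 94.2% | 9.9 |
| 90% | 72/80 | 81.2% to 95.6% | 14.3 |
| 90% | 36/40 | 76.3% to 97.2% | 20.9 |
| 80% | 128/160 | 73.0% to 85.9% | 12.9 |
| 80% | 64/80 | 69.6% to 88.1% | 18.6 |
| 80% | 32/40 | 64.4% to 90.9% | 26.6 |

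For a single disorder at 90%:

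| Correct / n | Exact 95% interval | Width (points) |
|---|---|---|
| 18/20 | 68.3% to 98.8% | 30.5 |
| 9/10 | 55.5% to 99.7% | 44.2 |

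(Widths are computed before rounding.)

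A perfect record does not remove the uncertainty. If every call is correct, the lower limit is 97.7% with 160 samples, 91.2% with 40 and 83.2% with 20. Knowing for each sample whether the call was right, which is what the Power Statement relies on, therefore does not replace an interval.

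**The case against.** The strongest reply is that the summary measure, the interval method and by-disorder reporting are commonly left to a statistical analysis plan, which may exist but is not at hand. As a general rule that is right, and silence alone would not be a finding. Here the protocol is not silent: it says no analysis will be done. A later plan that supplied an estimator would contradict it, so the sentence has to change either way.

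Second, the sentence belongs to a form item whose tick cannot be seen, and it may be leftover text. That is possible. But the explanation requested only of those who tick the box is there, and if the box was not ticked the sentence is still wrong and should go.

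Third, detection rates by known status could be obtained simply by counting calls. This stands in part: the reference standard and the per-sample result are fixed, so a usable table is within reach. What is missing is a commitment to report it, with its uncertainty.

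Fourth, the work is exploratory and pilot studies are excused. The form's note waives power analyses and endpoints for studies so labelled. This protocol does not use the label and does state endpoints, and the note does not waive the analysis of a stated endpoint. It does follow that a formal power calculation need not be demanded; the expected interval width is the least essential part of the remedy.

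Finally, the interval widths are generic binomial results on assumed counts and rates. That is true, and it limits what they show.

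**Conclusion.** The concern holds and must be fixed. The chart-review rationale is incompatible with the laboratory and diagnostic work described, and the no-analysis rule is incompatible with the primary endpoint and the comparison meant to answer it. Taken literally, the primary endpoint gets neither a detection rate nor a measure of uncertainty.

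The uncertainty left unreported would be about 10 to 27 points of interval width overall, across assumed rates of 90% and 80% and assumed counts of 160 down to 40 known-positive DBS. It would be about 30 to 44 points for a disorder with 20 or 10 samples at 90%, so by-disorder results can only be descriptive. The 160 is a count of subjects, not of DBS. Because the protocol sets no success threshold, these figures show precision that goes unstated, not a conclusion that would change.

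**What to change.** 1. Delete the sentence saying that no analysis will be performed, together with its chart-review rationale.
2. State the primary analysis: sensitivity of DBS profiling among known-positive samples with an exact 95% confidence interval, overall, and descriptively by disorder.
3. If known-negative DBS are included, report specificity among them with an exact 95% confidence interval. If there are none, say that specificity will not be estimated.
4. Replace the Power Statement with the numbers of known-positive and any known-negative DBS available, and the interval width expected for those numbers.

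The cost is protocol wording, a look-up of the DBS counts by known status, and a little analysis work; no new samples or procedures are needed. The price is candour: precision becomes explicit and less favourable, above all by disorder, and the protocol may have to say openly that specificity is not estimated.

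### Does a primary endpoint on dried blood spots fail because eligibility does not require a dried blood spot?

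*Protocol*

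**What the plan says.** - **Statistical Considerations, Power Statement.** Results are compared "with the known results of the DBS (negative or positive for an inborn error of metabolism) therefore it will be clear for each sample" if the profile gave the right answer. The Data Analysis Plan only refers back to this statement.
- **Endpoints, Primary.** "To evaluate whether untargeted metabolomics profiling on dried blood spots can detect inborn errors of metabolism".
- **Inclusion and Exclusion Criteria.** "All individuals with specimens in BGL or consented to future research under IRB 19-005187" are eligible, followed by "Exclusion Criteria: None".
- **Subject Information.** The form notes that "charts, records, images, or specimens are considered" subjects. Target accrual is 160, with no split by specimen type.
- **Study Design, Methods.** The work is the "analysis of existing DBS, fibroblast, serum, stool, and urine samples".
- **Background.** "The DBS will be the primary identifier". The same paragraph says that, "Based on the prior diagnosis of the samples", the profile will be examined for its ability to find the abnormality in DBS, serum, urine or fibroblasts.

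**The concern.** The endpoint and the comparison in the statistical section both depend on a DBS, but eligibility does not ask for one. Read literally, someone whose only stored material is a fibroblast line or a urine sample is eligible and counts towards the 160. That person has no DBS to profile and no known DBS result to compare with, so the statement that correctness will be clear for every sample would not be true of them. Because a specimen may itself count as a subject, the 160 could also be filled partly or largely with other specimen types.

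At stake would be the denominator of the primary endpoint. The detection rate on DBS could rest on far fewer than 160 results, and nothing in the criteria controls how many. The statistical section (known DBS result) and the Background (prior diagnosis) also name different references, which could leave the scoring of non-DBS samples unclear.

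**Working it through.** **1. Is there a planned figure to reproduce?** No. The 160 comes without a detection rate, power, interval width or DBS count. It can be neither reproduced nor shown to be missed.

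**2. Which reference applies to which specimen?**

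| Specimen | Reference in the Power Statement | Reference in the Background |
|---|---|---|
| DBS | known DBS result | prior diagnosis |
| Serum, urine, fibroblasts | none named | prior diagnosis |
| Stool | none named | not in the list |

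A serum, urine or fibroblast sample therefore has a stated reference. Only stool has none, and stool carries no endpoint of its own.

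**3. What does each sample mean in the Power Statement?** The sentence takes the known DBS result as its comparator and supports an endpoint defined on DBS. In that setting it reads naturally as each DBS. On this reading it is true and does not conflict with broad eligibility.

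**4. Who is meant to serve which objective?** Aims 1 to 3 cover fibroblasts, serum and urine as well as DBS, culture and measuring conditions, and samples altered before measurement. Subjects without a DBS are useful for those aims. Nowhere does the protocol say that all 160 enter the primary endpoint.

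**5. How much precision could be lost?** The inputs are 160 (Target accrual), an assumed share *s* with a DBS, and an assumed observed detection rate of 90% or 70%. The number of results is *n* = 160 × *s*. With *x* detected, the exact (Clopper-Pearson) 95% limits are the 2.5% quantile of Beta(*x*, *n* − *x* + 1) and the 97.5% quantile of Beta(*x* + 1, *n* − *x*).

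| Assumed *s* | *n* | Without DBS | 90%: *x*, interval | Width (points) | 70%: *x*, interval | Width (points) |
|---|---|---|---|---|---|---|
| 100% | 160 | 0 | 144, 84.3–94.2% | 9.9 | 112, 62.3–77.0% | 14.7 |
| 75% | 120 | 40 | 108, 83.2–94.7% | 11.5 | 84, 61.0–78.0% | 17.1 |
| 50% | 80 | 80 | 72, 81.2–95.6% | 14.3 | 56, 58.7–79.7% | 21.0 |
| 25% | 40 | 120 | 36, 76.3–97.2% | 20.9 | 28, 53.5–83.4% | 30.0 |

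**6. What the table does not show.** A detection rate is calculated on affected subjects only, and the Power Statement allows for negative as well as positive DBS results. The first row therefore holds only if all 160 subjects have a DBS and all are affected. The table shows how interval width depends on *n*. It does not measure a shortfall against the plan, because the plan sets no target.

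**The case for a change.** The strongest case for a change is that eligibility and accrual are settled in the protocol. A later analysis plan can define who is analysed, but it cannot ensure that a DBS is pulled for each subject. The remark about the DBS as primary identifier is ambiguous and is not a criterion. The target population of affected individuals is narrower than the inclusion line but does not require a DBS either. A short clause in the inclusion criterion would settle the matter cheaply, and it would have to come before samples are selected.

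Part of this stands. The criteria do not secure a DBS, the two references are not reconciled in the text, and the statement about each sample is loosely worded. But this does not show that following the plan gives a wrong or uninterpretable result. The specimens are existing ones or come from the linked protocol, so their type is known when they are chosen. Nothing indicates that any subject will lack a DBS. The Methods say that the linked protocol supplies specimens, so eligibility by consent alone, with nothing to measure, is a strained reading. A clause requiring a DBS of every subject would also narrow the intake for the other aims, so it would have to be limited to the primary endpoint. In that form it only states the analysis set that an analyst would use anyway.

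**Conclusion.** The concern does not call for a change. The criteria, the Power Statement and the Background are imprecise together, but a sensible analyst resolves them in one way: score the primary endpoint on subjects who have a DBS with a known result, judge the other specimens against the prior diagnosis, and report the number behind each. No result comes out wrong if this is done, and the broad intake suits the exploratory aims.

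The possible cost is a wider interval. At an assumed 90% detection rate the exact 95% width runs from 9.9 points with 160 results to 20.9 with 40; at 70% it runs from 14.7 to 30.0. These figures rest on assumed DBS shares, assumed rates and all scored subjects being affected. The protocol gives no specimen split, so the true loss could be zero, and it gives no precision target for any loss to breach.

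The conclusion rests on two readings: that each sample in the Power Statement means each DBS, and that 160 is overall accrual. It would change if the protocol had tied a stated power or precision to 160 DBS results, or if it gave a specimen split showing that few subjects have a DBS.

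### Comparison with the known DBS result shows whether profiling detected the disorder only if the call is made without sight of the diagnosis, and the protocol does not secure this

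*Protocol*

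**What the plan says.** The primary endpoint is "To evaluate whether untargeted metabolomics profiling on dried blood spots can detect inborn errors of metabolism". Under Statistical Considerations, the Power Statement sets out the scoring: "The results will be compared directly with the known results of the DBS (negative or positive for an inborn error of metabolism"), and concludes "therefore it will be clear for each sample whether the analysis showed the correct result". The next line is "Data Analysis Plan: As above", so this comparison is the whole analysis stated in the protocol.

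Three other places describe where the samples come from and how they are read:

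- Background, on the source: "Data in this study will be taken from anonime residual samples from Mayo Clinic patients with known diseases".
- Background, on the workflow, in a sentence about whether the profile reveals the known disorder: "Based on the prior diagnosis of the samples, metabolomics data will be collected and will be analyzed to see if the metabolomics profile can".
- Study Design, Methods, after the untargeted analysis: "We will then use the analysis to diagnose the inborn errors of metabolism in these individuals as well as identify biomarkers for these disorders".

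The table of subject identifiers marks a study number or code as the only internal identifier.

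**The concern.** The Power Statement moves from the existence of a known result to the conclusion that each reading can be judged right or wrong. That step needs a premise which the protocol does not supply: that the reader did not know the answer. An untargeted profile contains many analytes, and a reader told which disorder to expect knows where to look and how to settle a doubtful pattern. Agreement reached in that way may only confirm a label already held.

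The hypothesis section gives the goal as a screening and diagnostic platform, where the diagnosis is by definition not yet known. A favourable primary result from label-informed reading could not be carried over to that setting, and nobody could tell afterwards how much of the agreement came from the profile.

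**Working it through.** The protocol states no accuracy figure, so there is none to reproduce. The check is whether the text supports its own inference.

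**1. What the inference needs.** Agreement between call and known result measures detection if the call depends on the profile and not on the label. The reader must therefore make the call before seeing the diagnosis.

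**2. What the protocol provides.**

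| Place | What it establishes | Does it withhold the diagnosis from the reader? |
|---|---|---|
| Background, source of samples | Disease is known when samples are chosen | No |
| Background, workflow | Collection and analysis start from the prior diagnosis | No; it may mean sample selection only, but it permits informed reading |
| Methods | Profile first, then diagnosis and biomarker search | No; it gives an order of work, not what the reader knows |
| Power Statement | A result exists and is then compared | No; a result can precede the comparison and still be label-informed |
| Data Analysis Plan | Refers back to the Power Statement | No |
| Subject identifiers table | Data kept under a study code | No; the code protects identity, and a coded sample can still carry its diagnosis |

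No section mentions masking of readers or a call recorded before the diagnosis is revealed.

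**3. Direction.** A reader who leans on the label moves doubtful calls toward the known result. Each call changed in this way turns a disagreement into an agreement. The bias is therefore upward.

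**4. Size.** A figure would need the number of scored DBS, their split into positive and negative, the share of profiles that leave room for judgement, and how often an informed reader follows the label. None of these is given. The target accrual of 160 covers subjects across several specimen types and is not a count of scored DBS. Any percentage would rest wholly on assumption, so none is offered.

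**5. What masking needs in order to work.** The Subject Population entry reads: "The target population for this study includes anonime residual samples of individuals affected by inborn errors of metabolism". The Power Statement also speaks of negative results. If every scored DBS came from an affected person, a masked reader would still know that each sample is positive, and a bare normal/abnormal call would be protected by nothing. Masking is informative only if known negatives are mixed in and the call names the suspected disorder or pathway.

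**The case against.** The strongest reply is that this is silence, not error. Only the protocol is at hand, and reading procedures are often left to a statistical analysis plan or a laboratory procedure. The sentence in the Power Statement may mean no more than that every sample has a reference result to be checked against. The Methods derive the diagnosis from the profile, and the Background may refer only to how samples are chosen. The protocol also promises no sensitivity or specificity, only an answer to whether profiling can detect disease.

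Much of this stands, and it limits the point in three ways.

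- A reader might infer that profiles will be read with the diagnosis in view. The text permits this but does not say it.
- A reader might infer from the Methods that markers found in these samples will be used to score the same samples, which would add selection optimism. The sentence lists two uses of one analysis; it does not say that new markers feed the calls. That risk is conditional, and it does not support a requirement for cross-validation or for markers fixed beforehand.
- A reader might want a number for the bias. The documents supply no basis for one.

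The reply does not remove the point. The protocol draws a positive conclusion, that correctness will be clear, and its own description of the workflow leaves the necessary condition open. Masking is also a matter of conduct: it must be in place before profiles are read, and an analysis plan written later cannot restore it. The point does not rely on the form's remark that no statistical analysis will be performed, because the tick mark is not visible and the form then gives an analysis plan and endpoints.

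**Conclusion.** The point holds in a limited form. The conclusion that correctness is clear for each sample depends on calls made without sight of the diagnosis, and the protocol does not secure this. Unmasked reading is permitted, not proven. If it occurs, the primary detection result on DBS is biased upward by an amount that cannot be computed from the documents.

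This rests on two assumptions: that reading an untargeted profile involves some judgement, and that no unseen document already imposes masking. If calls came from a fully automatic rule that takes no account of the diagnosis, review bias would not arise, but the protocol describes no such rule. This is a cheap improvement, not a flaw that invalidates the study.

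**What to change.** Add to the Background and to Statistical Considerations:

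> DBS profiles, including the known-negative DBS, are read under the study code in mixed order by staff who do not hold the diagnosis key. For each sample the call (no disorder, or the suspected disorder or pathway) is recorded before the diagnosis is revealed, and only these recorded calls count toward the primary endpoint. Biomarkers identified after unmasking are exploratory and are not used to score the same samples.

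The Background sentence on the prior diagnosis should also say whether it refers to choosing samples or to reading them.

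The cost is small. A study code is already kept, so the change needs an existing team member who does not read profiles to hold the key, and a record of each call. The agreement figure may be less favourable, and a disorder recognised only through a marker found after unmasking could not count as detected in these samples. Biomarker discovery itself is unaffected.
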